**Background:**

Chronic constipation affects approximately 17% of the population worldwide and remains an important unmet need since patients are currently often dissatisfied with treatment. Current treatments which stimulate propulsive colonic motility or osmotic laxatives are successful in increasing stool frequency but are often associated with bloating, cramps and abdominal discomfort. Furthermore, such powerful treatments taken intermittently often create abnormal colonic contents and may result in alternation between diarrhoea and no stools. Many patients would benefit from a less powerful treatment which could be taken daily.

Kiwifruit offer such an alternative and have been shown to increase stool volume and frequency. The mode of action however is unclear. Kiwi is 3% fibre (approximately 1/3 insoluble) and contains around 3% nonstarch polysaccharide including pectins, hemicellulose and cellulose, with high water holding capacity 1.5 times that of ispaghula, a commonly used laxative. Two kiwifruit (150g) contain approximately 6.2gm of glucose and 6.5g fructose. The predominant protein is actinidin a cysteine protease. There are also a number of amines including serotonin and its precursor tryptophan, though these are present in only small amounts (serotonin 0.6g/100g). An unusual component is microcrystalline calcium oxalate monohydrate called rafides. While these dissolve in an acid pH it is unknown to what extent these would escape intact into the small intestine where their action might well excite a protective secretory response in enterocytes. Pig studies indicate that while the soluble component of kiwi fibre is well digested in the small bowel the insoluble component passes largely intact into the colon. Fermentation by microbiota lead to increases in ileal and faecal SCFAs.

Soluble fibre is a proven laxative softening stool and increasing stool frequency. Early studies in ileostomy patients showed that ispaghula increases ileal flow but until recently its mode of action in the intact colon was unclear. We have recently shown using novel non-invasive MRI techniques that ispaghula 3.5gm taken three times daily (t.d.s.) substantially increases small bowel water content in healthy volunteers and this is associated with an increase in colonic volumes and water content and an increase in the gastroileal response to eating, propelling larger amounts of ileal fluid into the ascending colon immediately after eating a 1000kcal meal.

Insoluble fibre in the form of 15g of bran has also been demonstrated to increase postprandial small bowel water content and accelerate small bowel transit.

It seems likely that kiwifruit soluble and insoluble fibre will lead to similar increases in small bowel water but whether the other components of kiwifruit such as actinidin and / or rafides will further enhance this is unclear nor what it effects is on colonic water and faecal viscosity.

***Value of MRI in assessing small bowel and colonic physiology***

Until recently defining the site of action of kiwifruit at the level of the small bowel and colon would require either invasive intubation studies or the study of ileostomists whose physiology may well differ significantly from the target population of healthy individuals. Using our recently developed and

[figure not shown]
validated novel non-invasive MRI techniques, the University can assess transit and fluid distribution in the small intestine. The University has also developed methods to assess colonic fluid, volumes and motility.

The University shall use these technique to measure fasting and postprandial small and large bowel water content and volumes to assess the relative significance of small intestinal and colonic secretion after kiwifruit.

The University has recently published data showing that IBS-D is associated with a constricted small bowel and accelerated transit, while constipation is associated with dilated small bowel and colon with slower transit, a novel insights which could only be obtained using the University's technique. Since this work, the University has further developed the technique so it can now assess not only colonic volumes but also the apparent water content from the relaxation time T1 parameter, which the University has recently showed correlates well with % water as assessed by freeze drying. The relaxation time T1 is simply the time constant with which the sample magnetization returns to baseline after excitation, a parameter well known since chemists started using it in the 1950s. The University can also assess whole gut transit time using its validated MRI transit markers, inert plastic capsules filled with a MRI-visible fluid.

The University has already performed an RCT of ispaghula and shown its ability to alter the freely mobile water content of the ascending, transverse and descending colon as assessed by our MRI techniques (See Figure 1).

### Ascending colon water content

**Figure 1:** images of bowel water content showing bright signal (e.g. fluid) in the colon of a subject after ispaghula treatment but no bright signal in the colon of the same subject after placebo

**Key questions to be addressed:**

Impact of kiwifruit on small and large bowel water content

**Aims:**

The aim is to evaluate the impact of kiwifruit on small and large bowel water content in order to explain the mechanism of action for kiwifruit on digestive comfort.

**Methodology:**

We will compare the effect of 3 days of 2 kiwifruit b.d vs placebo (28 gm maltodextrin drink providing 120kcal equal to that of 2 kiwifruit) daily.

**Study Design:*****(a) Study design***

This will be a randomised, placebo controlled, 2-way cross-over study in 15 healthy volunteers. The University will allow 2 weeks between studies to ensure return to baseline. In the unlikely event that these healthy subjects' bowel habit has not returned to normal the University will extend this by 1 or 2 weeks as required.

***(b) Study visits***

[figure not shown]
After a screening visit to confirm eligibility, study subjects will be randomised as to the test product schedule and be given the transit markers and instructions as to consume the test product two times daily for 2 days prior to the MRI study day on which they will also consume the kiwifruit as for the previous 2 days (see Figure 2). They will attend for the main imaging study on day 6 (see Figure 2).

Subjects will complete a daily stool diary documenting stool frequency and consistency using the Bristol Stool Form Scale during study days 1-6. They will visit the study site on the morning of Day 4 to receive their MRI marker capsules and kiwifruit or maltodextrin placebo. They will consume 2 kiwifruit b.d. starting on Day 4. At 9 am of the morning of Day 5 they will ingest 5 MRI transit markers as described below and note the time of ingestion. The University will contact subjects to remind them to take the pills and bring their test product packs with them as they will be required to take the same 3 doses on the study day 6. The markers will be imaged at 24 hours (baseline scan of Day 6).

On the main study day (day 6), the subjects will arrive fasted and undergo fasting scans before consuming that day's allocated test product with 250ml of water. After 30 minutes considered to be Time =0 they will consume a standard rice pudding meal as used in previous studies. They will then undergo serial scanning hourly for 8 hours taking the second dose of test product plus 250ml water at Time 180 minutes. At 380 minutes they will consume a second, larger test meal consisting of 400 g microwaveable macaroni cheese ready meal (Sainsbury), 100 g cheesecake slice (Sainsbury), and 250 mL bottled still water. The second test meal provides 1007 kcal, 43.4% from carbohydrate and 45.8% fat. The final scan will at time 420 minutes to assess the effect of ileal emptying on ascending colon water content. They will then be allowed home.

Figure 2

Study time lines

### (c) Subjects

**Inclusion criteria:** Healthy volunteers scoring within the normal range for bowel symptoms as assessed using the GSRS, aged 18-65 years.

#### **Exclusions:**

1. Inability to discontinue medication likely to alter GI transit.
2. Previous gastrointestinal surgery (excluding cholecystectomy and appendectomy).
3. Known inflammatory bowel disease, coeliac disease.
4. Known intolerance of kiwifruit.
5. Inability to discontinue drugs likely to alter gut transit.
6. Subjects considered by the investigator unlikely to comply with study protocol.

### (d) Test meal

220 grams of Sainsbury's creamed rice pudding, 34 grams of Sainsbury's seedless raspberry jam and 100 ml water. Total calorie content 290 kcal.

### (e) Test product allocation

This cannot be blinded but since the outcomes are objective and mechanistic this is less important than it would be if symptoms were the primary outcome. Subjects will be given either the kiwifruit or

unlabelled

sachets of maltodextrin which subjects will be told are dietary supplements. Analysis of the MRI images will be done by an investigator blinded as to the test product.

### **(g) Scanning Schedule**

Imaging will be carried out on a state-of-the-art, fully research dedicated 3.0T Scanner with a parallel imaging SENSE abdominal body receiver coil. A range of MRI sequences will be used to image the abdomen including:

- 1) A HASTE (half-fourier single shot turbo spin echo) sequence will be used to measure gastric volumes and hence assess gastric emptying. Slice thickness will be 10 mm with 24-30 axial slices acquired to cover the full stomach anatomy.
- 2) A high resolution A balanced gradient echo (called balanced turbo field echo, bTFE or trueFISP) sequence to acquire sagittal images of the contents of the ascending colon 8 slices 5 mm thick, 0.58 mm gap will be acquired to cover the AC anatomy.
- 3) A single shot, fast spin echo sequence (rapid acquisition with relaxation enhancement, RARE) to acquire coronal images with in-plane resolution interpolated to 0.78 mm x 0.78 mm and a slice thickness of 7 mm, with no gap between slices. This sequence yields high intensity signals from areas with fluid and little signal from body tissues and is used to measure bowel water content.
- 4) Colonic volumes are assessed using a coronal dual echo fast field echo sequence. Slices are acquired in two overlapping coronal stacks, each acquired in a breathhold. Colonic volumes are measured manually as previously described.. This sequence is also used to locate the position of the transit pills within the GI tract.
- 5) The University will assess T1 of colonic contents using previously published methods.

Data will be acquired on an expiration breath-hold with duration between 13 and 24 seconds depending on the sequence, monitored using a respiratory belt. Including set-up and imaging, the volunteers spend approximately 20 minutes inside the magnet for every time point and the rest of the time sitting upright in an adjacent room.

### **(f) Colonic transit**

The subjects will swallow 5 inert MRI transit marker capsules under the supervision of one of the study investigators with the study test meal. The marker capsules are made of Polyoxyethylene, the shape of a size 0 gelatine capsule, filled with 0.2 ml of 15 $\mu$ M Gadoteridol solution and sealed. Transit will be assessed from a scan performed 24 and 48 hours after marker ingestion. The transit will be assessed by scoring the position of the capsules according to the scoring system represented below in Figure 3A.

The weighted geometric centre of the 5 capsules at 24 and 48 hours will be calculated to give a measure of colonic transit time. To reduce the effect of outliers a weighting factor is calculated for each capsule depending on the difference of the capsule score from the median capsule score. For a difference of 0 and 1 the weighting factor was 1, for all differences larger than 1 the weighting factor is the inverse of the difference.

[figure not shown]
[figure not shown]

Figure 3a

3b

**Figure 3: (A) Scoring system (B) an examples of maximum intensity projection from a volunteer's T1-weighted TFE sequence scan 24 hours after swallowing 5 transit capsules showing the position of the capsules (indicated by the small arrows) within the colon. On these sequences the capsules appear bright.**

#### **Dietary guidelines and miscellaneous instructions:**

The day before each test day subjects will be asked to minimise changes in their usual lifestyle and to refrain from using alcohol, and doing strenuous exercise. They will be asked to keep a daily diary logging bowel symptoms, stool frequency and consistency for 1 week prior to the first study and during each subsequent study week up to day 7

Eating after 20.00 hour in the evening before the test day will not be allowed. Drinking water after waking on the study day and before reaching the study unit is not allowed. The volunteers will arrive at the test facility 30 minutes before starting the test.

During the test day, the volunteers will not be allowed to eat and drink anything else apart from the study test meals and drinks.

#### **Lower Dose Test**

At the end of the study we will scan a further 3 participants in exactly the same protocol however at a lower dose of kiwifruit (2 fruit once daily) to determine if the effect is still visible.

#### **Primary endpoint:**

Effect of Kiwifruit on Ascending colon T1 area under curve from time 0-420.

#### **Secondary endpoints:**

Effect of Kiwifruit on the following measures both fasting and postprandial AUC 0-420 minutes:

- 1) small bowel water content
- 2) ascending (AC), transverse (TC) and descending (DC) colonic volumes
- 3) Transit of markers through gut as assessed by the weighted position score at 24 h (WAPS24)
- 4) Colonic motility
- 5) Gastric emptying of test meal
- 6) T1 of AC and DC

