**Data analysis:**

[figure not shown]
Data will be assessed for normality and expressed as means  $\pm$  SE or median(range) if not normally distributed. Images will be coded and analysed blind as to allocation to avoid any bias in analysis. Measurements of the gastric emptying will be performed by manually drawing the region of interest on each slice using Analyze9 software (Biomedical Imaging Resource, Mayo Foundation, Rochester, MN, USA) and summing across all the slices to determine the total volume at each time point. In particular the gastric volumes will be analysed distinguishing the contents and the gas. The total gastric volume is the sum of the contents and the gas.

The University will assess small bowel water content from images acquired using the RARE sequences as previously validated. Colonic volumes will be assessed coronal dual echo fast field echo sequence.

The longitudinal relaxation time T1 in the ascending colon and, separately, in the descending colon will be measured using a single slice balanced Turbo Field Echo (bTFE) sequence with a preparatory 180 degrees inversion pulse applied before acquiring the imaging data . Data will be acquired from 8 different inversion times (TI) (time between inversion pulse and imaging pulses) ranging from 25 - 4925 ms. There will be a 10 second gap between each acquisition to allow the system to return to equilibrium. Small regions of interest will be drawn on the resulting images to calculate the mean signal intensity for the region at each different TI or TE. Care will be taken to exclude areas of gas or bowel wall. The data will then be fitted to a model of the signal evolution of the tissue after application of all the preparation and imaging pulses to determine the relaxation times.

The figure below shows the same example but for a T1 recovery curve with the fit to the data

shown as well on the right.

T1 colon data sets will be processed using custom written software in IDL® (Research systems Inc, Boulder, CO) to generate a region of interest in the ascending colon chyme avoiding small 'pockets' of free water (high intensity signal) if present. Then using the mean of this region at all the different echo times to calculate the T1 of the tissue using an in-house program.

Transit will be expressed as WAPS at 24hours (WAPS24) of the 5 markers and converted to transit time in hours using a nomogram (Figure 4) based on previous validation studies.

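### The AUC 0-420 rule, read literally, does not measure emptying of the test meal: the stomach is refilled at 180 and 380 min, and no other emptying summary is defined

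*Combined protocol and SAP*

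**What the plan says.** All references are to the combined protocol and SAP.

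- **Secondary endpoints.** The list is introduced by "Effect of Kiwifruit on the following measures both fasting and postprandial AUC 0-420 minutes". Item 5 is "Gastric emptying of test meal". No half-emptying time, percentage retained or shorter window is given for it anywhere.
- **Study Design, (b) Study visits.** Subjects "undergo fasting scans before consuming that day's allocated test product with 250ml of water". Then: "After 30 minutes considered to be Time =0 they will consume a standard rice pudding meal as used in previous studies". Hourly scans follow, with subjects "taking the second dose of test product plus 250ml water at Time 180 minutes". Next: "At 380 minutes they will consume a second, larger test meal". This meal is 500 g of food with 250 ml water, and "The second test meal provides 1007 kcal". The last scan is at 420 min.
- **(g) Scanning Schedule and Data analysis.** Emptying is inferred from gastric volumes outlined slice by slice at each time point. Contents and gas are analysed separately, and "The total gastric volume is the sum of the contents and the gas". No step separates the test meal from anything else swallowed.
- **Background and Methodology.** Two kiwifruit are put at 150 g. The placebo is a drink made from 28 g maltodextrin. Its made-up volume is not given, nor whether the 250 ml of water is part of it.

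**The concern.** An emptying measure should fall as the meal leaves the stomach. A total-volume AUC to 420 min adds together the first product dose, the test meal, a second product dose and a second meal. Most of it may therefore not be test meal, and any real change in emptying of that meal is diluted.

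The second meal is the same in both arms and would largely cancel in a crossover. The product loads are not the same: fruit plus water against a maltodextrin drink, once just before the window and once inside it. Two arms with identical emptying can therefore show different AUCs, and the plan would test that difference at p < 0.05. Because no other summary is written down, the window and the measure could also be chosen after the data are seen.

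**Working it through.** **Plan's own figure.** None exists for this endpoint. The only design calculation is for the primary endpoint (difference 88, SD 55, n = 15). Taken as a paired t test it gives 99.99% power, which agrees with the stated >90%. This point does not depend on it.

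**Timeline.** Time after the second dose: (420 − 180)/420 = 57% of the window. Time after the second meal: (420 − 380)/420 = 10%. On scans at 0, 60, …, 420 min, those at 240, 300, 360 and 420 (4 of 8) follow the second dose and one (420) follows the second meal.

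**Illustrative model.** Each intake j of size m_j at time t_j empties exponentially at the same rate in both arms:

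V(t) = Σ m_j · 2^(−(t − t_j)/h)

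AUC = 60 · [½V(0) + V(60) + … + V(360) + ½V(420)]

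*From the documents:*
- test meal at 0 min: 220 + 34 = 254 g food and 100 ml water
- product at −30 and 180 min: 150 g fruit, or 28 g maltodextrin, each with 250 ml water
- second meal at 380 min: 500 g food and 250 ml water

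*Assumed:*
- 1 g = 1 ml, and intake is instantaneous
- food half-time h is 45, 60 or 90 min; water half-time is 15 min, 30 min or equal to food
- the second dose comes just after the 180 min scan, and placebo is taken at both dose times

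**One case in full (food 60 min, water 30 min).** Test meal: 60 × 254 × 1.4883 + 60 × 100 × 0.8333 = 22,681 + 5,000 = 27,681 ml·min.

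| Arm and reading of the drink | Dose 1 | Test meal | Dose 2 | Meal 2 | Total |
|---|---|---|---|---|---|
| Kiwifruit | 15,721 | 27,681 | 13,108 | 12,426 | 68,936 |
| Placebo: 28 g + 250 ml plain water | 8,018 | 27,681 | 6,474 | 12,426 | 54,599 |
| Placebo: a further 250 ml | 14,267 | 27,681 | 11,425 | 12,426 | 65,799 |
| Placebo: 268 ml solution emptying as food | 16,922 | 27,681 | 14,573 | 12,426 | 71,602 |

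The ratios are 68,936/54,599 = 1.26, 68,936/65,799 = 1.05 and 68,936/71,602 = 0.96. On kiwifruit the test meal is 27,681/68,936 = 40% of the AUC, and intake from 180 min onward is (13,108 + 12,426)/68,936 = 37%.

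**Over all nine half-time combinations**, with no true difference in emptying:

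| Reading of the placebo drink | Kiwifruit/placebo AUC ratio | Test meal share (placebo) | Later intake share (placebo) | Largest arm difference in fraction remaining, 0-180 |
|---|---|---|---|---|
| 28 g + 250 ml plain water | 1.17-1.40 | 40-64% | 28-38% | 0.04 |
| A further 150 ml | 0.96-1.35 | 32-62% | 28-40% | 0.07 |
| A further 250 ml | 0.85-1.32 | 29-60% | 28-40% | 0.08 |
| 268 ml solution emptying as food | 0.81-1.22 | 37-42% | 35-38% | 0.08 |

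On kiwifruit the test meal share is 33-46% and the later share 32-39%. Under the kiwifruit load and the first placebo reading, modelled contents rise from 3-142 ml at 360 min to 311-641 ml at 420 min, so the curve is not an emptying curve.

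**Is a shorter window enough?** No. Raw AUC 0-180 still has a ratio of 1.15-1.29 under the first placebo reading and 0.86-1.18 under the last, because of the first dose. Dividing by the first postprandial volume leaves the much smaller differences in the last column.

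**The case against.** **The header is loose drafting.** It also covers the 24 h marker score, which has neither a fasting value nor an AUC, and a fasting value for emptying of a meal has no meaning. The sponsor may not have intended AUC 0-420 for item 5. This stands, and it lowers confidence in the literal reading. It does not remove the point, because no other emptying summary is written.

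**The data are usable.** Volumes are taken at each time point, and the plan includes a two-way ANOVA over time with corrected post-hoc tests, so early scans could be compared on their own. A reader might infer that the trial cannot measure gastric emptying. The documents do not support that: the limit lies in the 0-420 summary, not in the images. The ANOVA does not, however, name the scans or the quantity that define emptying.

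**Direction.** A reader might infer that kiwifruit's AUC must come out higher because more mass is swallowed, giving a false finding of slowed emptying. That follows only if the placebo is 28 g with 250 ml of plain water. The plan calls it a drink without giving its volume, and other readings give ratios on both sides of 1. The directional claim is not supported.

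**Gas.** Contents are already to be analysed apart from gas, so gas is not a gap in the plan.

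**Scope.** This is one of six secondary items. The documents do not say that gastric emptying is needed to interpret small bowel water.

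**Conclusion.** The point holds as a limited one about a single secondary endpoint. As written, the AUC 0-420 of gastric volume does not measure what item 5 names. The timeline part (4 of 8 scans after the second dose, one after the second meal) needs only the hourly grid and a 180 min scan taken before the dose.

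The sizes are illustrative. Across both arms the test meal supplies about 29-64% of the AUC and later intake about 28-40%, and the between-arm ratio under equal emptying is about 0.8-1.4. They rest on exponential emptying, the assumed half-times and the assumed readings of the placebo drink. The direction of bias is not known.

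The primary endpoint is ascending colon T1, and neither it nor the sample size is affected. Severity is low to moderate.

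**What to change.** 1. Take item 5 out of the AUC 0-420 rule.
2. Analyse gastric contents, without gas, from the first postprandial scan to the last scan completed before the second product dose. Express them as percent of the first postprandial volume remaining, or as a half-emptying time.
3. Name the endpoint *emptying of test meal plus first test product*.
4. Report gastric volumes at later scans descriptively.
5. State whether the 180 min scan precedes the dose, and the made-up volume of the placebo drink. Reconcile hourly scanning for 8 hours with a last scan at 420 min (7 hours). The Study visits section also mentions three doses on the study day but times only two; these statements must be reconciled.

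The cost is a wording change, since the scans are already scheduled. Only three or four hourly points will support the estimate, depending on when the 180 min scan falls. The first product dose also stays in the measure: under the same assumptions the arms can still differ by up to about 0.08 in fraction remaining with no true difference in emptying.
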